### Study Schematic

Due to the early termination of this study, the duration of study treatment and performance of the protocol specified termination procedures will not be completed according to the design of the

protocol as previously described. All subjects still receiving study medication at the time of study termination by sponsor will be contacted by the site promptly, instructed to stop dosing, and will be asked to return for an End of Treatment a (EOT) Visit. When the data for that EOT visit has been entered into the EDC system, the treatment code will be provided to the study site. Subjects treated with avagacestat will be scheduled for the Post Treatment/Study Termination Safety Follow-up Visits (to occur 4 Weeks, 12 Weeks, and 24 Weeks after last dose). Subjects who were randomized to the placebo arm, and those enrolled in the observational cohort will be advised of their treatment group and told that no further assessments are required.

Avagacestat-treated subjects should be scheduled for a 4 Week, 12 Week, and 24 Week Post Treatment Safety Follow-up Visit as outlined in Table 6.1-4. All attempts should be made to complete the three Post Treatment/Study Termination Safety Follow-up Visits.

Avagacestat treated subjects participating in the long-term safety follow-up phase **for 12 weeks or less** should be scheduled for a 12 Week Post Treatment/Study Termination Safety Follow-up Visit, as well as for a 24 Week Post Treatment/Study Termination Safety Follow-up Visit for a comprehensive skin examination by a dermatologist (or dermatologic physician's assistant in the United States);

Avagacestat-treated subjects participating in the long-term safety follow-up phase **for greater than 12 weeks** should only be scheduled to return for the 24 Week Post Treatment/Study Termination Safety Follow-up Visit for a comprehensive skin examination by a dermatologist (or dermatologic physician's assistant in the United States).

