#### 8 STATISTICAL CONSIDERATIONS

# 8.1 Sample Size Determination

The primary endpoint of this study is safety and tolerability. The sample size of 135 subjects per group is chosen empirically rather than based on the statistical power consideration. However, it should be noted that with 135 subjects per dose group, the probability of observing at least one specific AE is satisfactorily high at each dose group if the true event rate of that AE is within the commonly observed ranges, as shown in Table 8.1-1 with a list of assumed true event rates. For example, the probability of observing at least 1 specific AE is 98% at each dose group if the true event rate of that AE is 3% (Table 8.1-1). Table 8.1-2 shows the probability of observing at least one event difference assuming different event rates for each treatment group. In addition, the 95% exact confidence interval of 10% (13 events out of 135 subjects) event rate in each group is (0.05, 0.16).

Table 8.1-1: Probability of Observing a Given Adverse Event

Assumed AE incidence rate	Probability of observing at least 1 AE out of 135 patients a
0.1%	12.6%
0.5%	49.1%
1%	74.2%
2%	93.5%
3%	98.4%

Assumes a distribution of Binomial (n = 135, probability of event given in the first column).

Table 8.1-2: Probability of Observing at Least One Incidence Difference

AE incidence rate (%) for Placebo		AE incidence rate (%) for Active						
		0.1	0.5	1	2	3		
	0.1	22.3%						
	0.5	51.4%	60.9%					
	1	73.2%	71.8%	74.1%				
	2	92.0%	87.0%	83.2%	82.2%			
	3	97.6%	95.0%	90.9%	86.1%	85.6%		

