# 8.4.3 Efficacy Analyses

Confidence intervals will be reported at the 95% level, if not otherwise specified.

In order to assess the predictive value of baseline CSF biomarkers (A $\beta$ 40, and A $\beta$ 42, total Tau, total Tau/A $\beta$ 42 ratio, and phosphorylated Tau) on progression to dementia, the relationship between each of CSF biomarker and time to progression to dementia will be assessed by separate stratified Cox proportional hazards model on the Randomized Sample. The Cox model will include treatment, age, gender, education and individual baseline biomarker as covariates and ApoE4 status and baseline status of acetylcholinesterase inhibitor treatment as stratified variables. The parameter estimate and 95% CI for the hazard ratio for one unit increase in the biomarker will be reported. Patients who do not have progression to AD will be censored on their last visit date.

In order to validate  $A\beta42$  screening cutoff point of 200 pg/mL, stratified logistic analysis will be carried out on the combined dataset of placebo group and observational cohort. The logistic model will have progression to AD (yes/no) as a binary dependent variable and age, gender, education and  $A\beta42$  screening value as covariates and ApoE4 status and baseline status of acetylcholinesterase inhibitor treatment as stratified variables.

Time to progression to dementia will be obtained from Kaplan-Meier maximum likelihood estimates for each treatment group on the Randomized Sample.

For each of the continuous efficacy outcome measurements (CDR-SB and ADAS-Cog, etc), the change from baseline to post-baseline scores (up to 24 months) over time from the Randomized Sample will be analyzed using a linear mixed effects model repeated measures (MMRM) with maximum likelihood estimation. The model will include treatment, time, baseline primary efficacy score, the interaction between baseline primary efficacy score and time, baseline MRI volume, APOE status, baseline status of acetylcholinesterase inhibitor treatment and the interaction between treatment and time as covariates. Time is classified into months (3, 6, 9, 12, 15, 18, 21, and 24) and treated as a categorical variable. An unstructured covariance matrix will be used to represent the correlation of the repeated measures within each subject. Model based adjusted mean change score from baseline (LS means) at each study month and 95% CI for the treatment difference will be reported.

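### Section 8.4.3 fixes the MMRM to maximum likelihood rather than REML, which makes its standard errors and 95% confidence intervals slightly too narrow

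*Protocol*

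**What the plan says.** Section 8.4.3 of the protocol analyses change from baseline in CDR-SB, ADAS-cog and the other continuous efficacy outcomes with a "linear mixed effects model repeated measures (MMRM) with maximum likelihood estimation". The rest of the model is set out in the same paragraph:

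- **Visits:** "Time is classified into months (3, 6, 9, 12, 15, 18, 21, and 24) and treated as a categorical variable".
- **Covariance:** "An unstructured covariance matrix will be used to represent the correlation of the repeated measures within each subject".
- **Fixed effects:** treatment, time, their interaction and the baseline score, and also "the interaction between baseline primary efficacy score and time, baseline MRI volume, APOE status, baseline status of acetylcholinesterase inhibitor treatment".
- **Output:** "Model based adjusted mean change score from baseline (LS means) at each study month and 95% CI for the treatment difference will be reported".

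The paragraph does not name a degrees-of-freedom method or a standard-error method. On the number of subjects, Section 8.1 states: "The sample size of 135 subjects per group is chosen empirically rather than based on the statistical power consideration". Section 8.5 adds that none of the efficacy endpoints is primary.

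**The concern.** ML estimates the covariance matrix as if the fixed effects were known, so the variances are biased downward. REML removes most of this bias. With a single outcome and ordinary regression, the ML variance divides the residual sum of squares by n, and the REML variance divides it by n minus the number of regression parameters. The MMRM behaves in a similar way visit by visit. The bias is larger where fewer subjects contribute, which is at the late visits.

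At stake is the stated coverage of the intervals for the treatment difference, most of all at month 24. The error runs in one direction only: the intervals look more precise than they are. The estimator is written into the protocol, so an analysis plan that used REML would have to depart from it.

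**Working it through.** **Inputs from the protocol.** 135 subjects per arm, so 2 × 135 = 270 (Section 8.1); 8 visits, unstructured covariance and the covariates listed (Section 8.4.3); 95% intervals (Section 8.4.3).

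**Size of the model.** Covariance parameters: 8 × 9 / 2 = 36. Fixed effects: 8 (time) + 8 (treatment by time) + 8 (baseline by time) + 3 (MRI volume, APOE, cholinesterase inhibitor) = 27. About 6 of them bear on any one visit: intercept, treatment, baseline and the three covariates.

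**The plan's own figures.** The protocol gives no power, effect size or interval width for the MMRM, so there is nothing of that kind to reproduce. Its sample-size figures concern adverse events. Table 8.1-1 recomputes to 12.6, 49.2, 74.2, 93.5 and 98.4%, and the exact interval for 13/135 to (0.052, 0.159). Both agree with the text apart from rounding, and neither bears on this point.

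**Simulation of the stated model.** Assumptions: 135 per arm; SD rising over time; correlation 0.85 between adjacent visits, decaying with distance; monotone dropout that depends mildly on the last score; 1,500 trials per scenario. Each trial was fitted by ML and by REML. Month-24 results:

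| Assumed retention at month 24 | ML SE / REML SE | Coverage, ML, t(264) | Coverage, REML, t(264) |
|---|---|---|---|
| 100% | 0.993 | 95.9% | 96.0% |
| 80% | 0.992 | 94.7% | 95.0% |
| 70% | 0.992 | 94.1% | 94.4% |
| 50% | 0.990 | 94.1% | 94.3% |
| 30% | 0.985 | 93.9% | 94.4% |

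The Monte Carlo standard error of each coverage figure is about 0.6 points. With the same t reference for both methods, ML costs 0.5 points of coverage or less.

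**Second simulation, with harsher dropout** (250 replicates). Losses of 5%, 12% or 20% per visit leave about 190, 110 or 57 subjects at month 24, that is 70%, 41% or 21% of 270. The ratios are 0.990, 0.986 and 0.977. If the REML interval is taken as nominal, a ratio of 0.977 gives a two-sided error of 2 × (1 − Φ(1.96 × 0.977)) ≈ 5.5% in place of 5%.

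**Adding the choice of reference distribution.** If ML were also paired with a normal critical value, and compared with REML and t on (completers − 6) degrees of freedom, the first simulation gives width ratios from 0.988 (full retention) to 0.969 (30% retention). Coverage then falls by 0.1 to 0.8 points. This part is conditional, because the protocol does not say which reference distribution is used.

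**Rough cross-check.** Using only the subjects seen at one visit, the ratio is √((n − 6)/n): √(264/270) = 0.989 at n = 270, and √(75/81) = 0.962 at n = 81. These shortfalls are larger than the simulated ones (0.993 at full retention and 0.985 at 30%). The approximation ignores what earlier visits contribute, so it serves as a pessimistic bound.

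**The case against.** The strongest reply is that ML with an unstructured covariance is a valid and consistent estimator, that 135 per arm is not a small sample, and that a 1% to 2% shortfall in a standard error on exploratory endpoints will not mislead anyone. On size, this stands. With full retention the simulated ML interval covered 95.9%, so no practical harm is visible there.

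Several stronger readings are tempting, and the documents do not support them:

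- **That every efficacy interval is too narrow.** Section 8.4.3 also plans Cox models, a logistic model and Kaplan-Meier estimates. The choice between ML and REML does not touch them.
- **That the protocol rules out small-sample degrees of freedom.** It is silent on this, and the detail commonly sits in the statistical analysis plan, which is not at hand.
- **That a nominal 5% test would run near 7%.** A figure of 6.8% follows only from the per-visit bound at 60 subjects with a normal reference. Simulation at 57 subjects gives a standard-error shortfall of 2.3%, less than half of the bound's 5%.
- **That the late visits are known to be badly depleted.** Section 4.1 records that "Due to the early termination of this study, the duration of study treatment and performance of the protocol specified termination procedures will not be completed". It gives no number reaching month 24, and with treatment planned for 104 to 220 weeks some subjects may have passed month 24 before termination.
- **That the biomarker model in Section 8.4.8.1 has the same error.** That section does not name ML.
- **That the figures above describe PROCOG.** It is collected at US sites only and on a sparser schedule, so the simulations with 270 subjects and eight visits do not represent it.

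What remains is that the protocol names the estimator, the bias has a known direction, and a standard alternative removes most of it.

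**Conclusion.** The point holds in a limited form. Under ML, the MMRM standard errors at month 24 are about 0.7% too small with full retention, about 1.5% too small with 30% of subjects left, and about 2.3% too small with about 21% left. Coverage falls by less than 1 percentage point, even when a normal reference is added at 30% retention. These sizes rest on assumed retention, SD and correlation patterns. The direction of the bias does not rest on them. The affected outcomes are not primary and the sample size was not based on them, so the severity is minor.

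**What to change.** In Section 8.4.3, change the estimation method of the MMRM from maximum likelihood to restricted maximum likelihood (REML), preferably with Kenward-Roger degrees of freedom. That adjustment is built on REML, so the two belong together. The rest of the model can stay as written.

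The cost is one phrase and a standard software option, with no new data. REML alone widens the month-24 intervals by about 0.7% (1/0.993) at full retention and 2.4% (1/0.977) at about 21% retention. Compared with ML and a normal reference, REML with a t reference widens them by about 1.2% (1/0.988) at full retention and 3.2% (1/0.969) at 30% retention. If the statistical analysis plan already specifies REML, the protocol wording should be brought into line with it.

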# 8.4.4 Pharmacokinetic Analyses

The BMS-708163 plasma concentrations obtained by sparse and intensive sampling of individual subjects will be used to build a population PK model to estimate PK parameters (eg, CL/F, Vd/F, and ka). Summary statistics will be provided for all drug concentration data and for PK parameters following intensive PK sampling. Possible covariate effects on PK parameters (eg, gender effect on CL/F) may be identified and quantified. The influence of symptomatic co-medication (ChEI) on PK parameters may also be explored. Using model-based estimations, the PK parameters will be used to compute individual exposure measures (eg, AUC, Cmax, Cmin). The PK data derived from this study may also be pooled with data from other studies to refine the model-based analysis to optimize dose selection for Phase 3. This population analysis will be presented separately.

For subjects having intensive pharmacokinetic sampling, individual subject pharmacokinetic parameter values (eg, Cmax, Tmax, Cmin, AUCTAU) will be derived by non-compartmental methods by a validated pharmacokinetic analysis program.

The CSF samples taken during the study will also be assayed for BMS-708163.

# 8.4.5 Pharmacodynamic Analyses

The corrolation between BMS-708163 exposure and CSF concentrations of A $\beta$ 40, A $\beta$ 42, tau, and phosphorylated tau, and/or their reductions from baseline will be explored. Relationships between BMS-708163 exposure measures and efficacy scores (eg, ADAS-cog changes from baseline) will be explored. Similar exploratory analyses may be performed for other cognitive and/or safety endpoints. If warranted, CSF biomarker response and safety/efficacy (ie, cognition) events and their relation to free drug concentrations may be explored as well based on the fraction bound to plasma proteins.

# 8.4.6 Pharmacogenomic Analyses

Details of the pharmacogenomics analyses are noted in Amendment 01.

#### APOE:

Part of the efficacy analysis will make use of an analysis of covariance (ANCOVA) model, controlling for the APOE4 genotype (positive vs negative). This takes into account published clinical Phase 2 study findings with rosiglitazone indicating APOE genotype related treatment differences  $^{56}$  as well as clinical Phase 2 indicating genotype related treatment differences with the humanized A $\beta$  antibody Bapineuzumab.  $^{57}$ 

#### **CYP Enzyme Genotyping:**

Metabolism of BMS-708163 is primarily mediated via CYP3A4, CYP2C9, and CYP2C19, while the involvement of additional CYP enzymes is possible. In order to better understand PK

variability, relations between polymorphisms of CYP enzymes, in particular CYP2C9 and 2C19, and exposures will be explored.

# 8.4.7 Outcomes Research Analyses

The mean change from baseline to each scheduled visit in PROCOG will be analyzed similarly to that for efficacy endpoint.

# 8.4.8 Other Analyses

#### 8.4.8.1 Biomarker Analyses

The mean change from baseline to each scheduled visit in the proposed biomarker measures (CSF biomarkers, plasma biomarkers and Volumetric MRI) will be analyzed based on Safety Sample. The analysis will make use of ANCOVA model, controlling for key covariates (APOE4 genotype, and concurrent AD medication use) and adjusting for corresponding baseline.

Specifically, for plasma TFF3 or CSF and plasma A $\beta$ 40 and A $\beta$ 42, the ANCOVA model will be applied to the log-transformed percentage of baseline measures. If multiple post-treatment time points were measured, a linear mixed effect model with fixed dose effect and time effect (repeated measures) will be used for the analysis.

For whole blood mRNA genes (HES-1), the gene expression level will be normalized to an internal housekeeping gene (eg, GAPDH) before applying statistical analysis. The change from baseline of the normalized gene expression levels will be fitted into the ANCOVA model.

#### 8.5 Interim Analyses

Interim analysis may be performed on safety and efficacy parameters, CSF biomarkers, and clinical PK and PD data to help inform the development of Phase 3 protocols. The results of these analyses will be presented to a limited number of BMS employees in an unblinded manner. Investigators and subjects will remain blinded. No adjustment to significance levels for the final analyses will be made due to this interim analysis because none of the efficacy endpoints is primary and the sample size determination is not based on efficacy.

Additional details of the interim analysis will be described in the statistical analysis plan.

#### 9 ADMINISTRATIVE SECTION

#### 9.1 Compliance

# 9.1.1 Compliance with the Protocol and Protocol Revisions

The study shall be conducted as described in this approved protocol. All revisions to the protocol must be discussed with, and be prepared by, BMS. The investigator should not implement any deviation or change to the protocol without prior review and documented approval/favorable opinion from the IRB/IEC of an amendment, except where necessary to eliminate an immediate hazard(s) to study subjects. Any significant deviation must be documented in the CRF.
